
Part Two Study Objective: The second part of the study is a prospective, parallel-group, randomized, controlled pilot study examining the effect of BiLevel therapy (and NOT if needed) vs. NOT alone in patients with overlap syndrome (20 subjects in each treatment arm).

Study Intervention: This will be done in 40 subjects in overlap syndrome group only who provide informed consent (20 subjects in each treatment arm). Randomization of overlap syndrome subjects to nocturnal BiLevel therapy (plus oxygen if needed based on saturations <88% while on stable bi-level settings), and NOT only will be done using sequentially-numbered, opaque, sealed envelopes using 1:1 allocation ratio. Regular therapy with COPD medications including long-acting anticholinergic medications and inhaled corticosteroids will be continued as advised by the treating pulmonologist. Only COPD subjects with stable clinical course during the duration of study intervention will be called for follow-up visits as any COPD exacerbations during the course of study intervention may potentially confound the follow-up study results. The time commitment for this initial visit will require up to 2-3 hours of the subjects time.

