Follow-up visits: The first follow-up visit will be done 2 weeks after starting treatment to ensure compliance and determine any discomforts due to treatment. At this visit phlebotomy will be done to take blood samples for venous gas analysis. Subjects will be asked to complete all questionnaires as outlined in the baseline visit. Second follow-up visit will be done 3 months after starting treatment to ensure compliance with treatment and determine any study related discomforts. Subjects will be asked to complete all questionnaires and cognitive function testing as outlined in the baseline visit. The final follow-up visit will be done 6 months after starting study treatment. Throughout the course of the study, regular telephone contact will be maintained by the study staff to ensure adherence to therapy and to address issues as they arise. At this final follow-up visit, all the tests done at baseline visit (except PSG) will be repeated as well as all afore mentioned questionnaires and cognitive function testing. This pilot study will generate preliminary data for a multi-center clinical trial with longer duration of PAP therapy and mortality, hospitalizations or COPD exacerbations as outcomes, if we find encouraging results. If the subject is called for follow-up visits, first follow up visit will require a time commitment of 15-20 minutes (2 week mark of starting treatment) for and the other two follow up visit will require a time commitment of 25-30 minutes (one at the 3-month mark of starting treatment and one final follow up visit). During the course of the 2 week, 3 month and 6 month periods between follow up visits, study staff may contact the patient to ensure adherence to therapy and address issues as they arise. While these phone call encounters may vary in time based on the subject's needs, typically they should require no more than 5-10 minutes of the subject's time.

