Study endpoints: Primary endpoint: RVEDV (estimated by cardiac MRI) across the three study groups, and following intervention in the overlap syndrome patients in the randomized trial. Secondary endpoints: RVESV, RVEF, RV mass index, right atrial pressure, PA pressure and blood flow, indices of RV geometry, thickness and interdependence, LVEDV, LVESV, LVEF, LV wall motion, , extracellular volume, coronary blood flow, endothelial function (EndoPAT), serum complete blood cell counts (with differentials), serum renal profiles, pharyngeal lavage cell counts and differentials, serum and pharyngeal lavage inflammatory biomarkers (CRP, TNF-alpha, IL-6, P-selectin, ICAM-1), sympathetic activity (measured by urinary catecholamine excretion), HRQOL score and BODE index.

To offset transportation costs, parking costs and use of the volunteer's time, subjects will receive \$150.00 for the overnight sleep study and an additional \$100.00 for the MRI for a total of \$250.00 upon completion of all tests in Part I. Study staff might ask the subject to return for a second overnight sleep study visit in the event the

data is of poor signal quality or we were unable to obtain sufficient data to complete analysis. If the subject agrees to return for a repeat study, he/she will be compensated \$150.00 for their time and transportation.

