14. POTENTIAL RISKS

As we anticipate minimal risk from our studies, we doubt any subject will need to be removed or excluded from the study.

There is a very small risk of loss of subject confidentiality. We will protect all subject information to the best

of our ability so this will not happen.

Phase One Study

We believe the risks and discomforts to be small. All patients will be screened for standard contraindications (e.g. implanted device and foreign bodies) for cardiac MRI. If contraindicated, patients will not be enrolled to the study. All participants will be given a full description of the risks associated with MRI scanning as part of informed consent process. Gadolinium contrast, which is required for cardiac MRI, has been associated rarely with the syndrome of nephrogenic systemic fibrosis in patients with moderate to severe kidney diseases. Therefore, moderate or severe kidney disease is one of the exclusion criteria to minimize the potential risk. Small number of patients may experience anxiety or claustrophobia due to the confined space of MRI scan. However, the anxiety or claustrophobia often, if not always, resolves after termination of the scan. We and other investigators have accomplished similar studies without incident.

Phase Two Study

We believe the risks and discomforts to be small. All patients will be screened for standard contraindications (e.g. implanted device and foreign bodies) for cardiac MRI. If contraindicated, patients will not be enrolled to the study. All participants will be given a full description of the risks associated with MRI scanning as part of informed consent process. Gadolinium contrast, which is required for cardiac MRI, has been associated rarely with the syndrome of nephrogenic systemic fibrosis in patients with moderate to severe kidney diseases. Therefore, moderate or severe kidney disease is one of the exclusion criteria to minimize the potential risk. Small number of patients may experience anxiety or claustrophobia due to the confined space of MRI scan. However, the anxiety or claustrophobia often, if not always, resolves after termination of the scan. We and other investigators have accomplished similar studies without incident. Nocturnal oxygen therapy (NOT) and BPAP therapy have both been used in COPD patients in numerous previous research studies without significant reportable risks. NOT and BiLevel therapy will be closely followed and titrated to minimize any discomfort or adverse effects.

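### The randomised pilot does not list exacerbations, hospitalisations or deaths for recording by arm, although they are the outcomes of the larger trial it is meant to inform

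*Protocol*

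**What the plan says.** Three parts of the protocol's Section 9 bear on this, together with one statement of purpose.

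- **Follow-up visits.** "The first follow-up visit will be done 2 weeks after starting treatment to ensure compliance and determine any discomforts due to treatment". The second visit comes "3 months after starting treatment to ensure compliance with treatment and determine any study related discomforts". The last is fixed by "The final follow-up visit will be done 6 months after starting study treatment", with no safety purpose stated. The visits also include venous gas at 2 weeks, questionnaires at every visit, cognitive tests at 3 and 6 months, and a repeat of all baseline tests except the sleep study at 6 months. Telephone contact runs through the whole study, for adherence and for problems that come up.
- **Study endpoints.** RVEDV is primary. The secondary list covers imaging, endothelial function, blood and lavage measures, and ends with "sympathetic activity (measured by urinary catecholamine excretion), HRQOL score and BODE index". It contains no clinical event.
- **Study Intervention (Part Two).** Only patients whose COPD stays clinically stable are called for follow-up visits. The reason given is that an exacerbation might confound the follow-up results.
- **Purpose.** The pilot is to supply preliminary data for a longer multi-centre trial with "mortality, hospitalizations or COPD exacerbations as outcomes, if we find encouraging results". Section 7 (Limitations of prior literature) names the same three outcomes.

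**The concern.** The events that matter most to the next trial are not among the data that this one undertakes to collect. Staff must learn of each exacerbation to apply the stable-course rule, but the plan uses that knowledge to decide who is invited to a visit and gives it no place as an outcome.

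An exacerbation after randomisation may itself be an effect of treatment. Section 7 says that earlier studies of nocturnal bilevel treatment of hypercapnia in COPD gave conflicting results, so the direction of any effect on clinical events is open. If one arm had more exacerbations, those patients would not be called for visits and nothing in the plan would require their events to be counted. The nearest clinical measures on the list, quality of life and BODE, depend on those same visits.

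An analysis plan cannot repair this later, because it can only analyse what was collected.

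**Working it through.** The protocol states no event rate, power or effect size for Part Two, so there is no figure to reproduce. The check is a reading of the text, followed by arithmetic for scale.

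**1. Where each event appears in the plan for Part Two**

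| Event | Endpoint list | Visit or call content | Elsewhere |
|---|---|---|---|
| COPD exacerbation | no | no | reason not to call for visits (Section 9); outcome of next trial (Sections 7, 9) |
| Hospitalisation | no | no | outcome of next trial (Sections 7, 9) |
| Death | no | no | outcome of next trial (Sections 7, 9) |

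Section 14 says that both treatments will be followed closely and titrated to limit adverse effects. It sets no rule for recording events or reporting them by arm.

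**2. Deaths to be expected (scale only)**

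Inputs from Section 7: all-cause mortality of 42.2% in untreated overlap syndrome and 24.2% in COPD only, after a median of over 9 years. Assumptions: constant hazard and exactly 9 years.

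- Untreated overlap: −ln(1 − 0.422)/9 = 0.0609 per year. The 6-month risk is 1 − exp(−0.0609 × 0.5) = 3.0%. Expected deaths are 40 × 0.030 = 1.2, or 0.6 per arm. The chance of at least one death in 40 is 1 − 0.970^40 = 70%.
- COPD only: −ln(1 − 0.242)/9 = 0.0308 per year. The 6-month risk is 1.5%, and expected deaths are 40 × 0.0153 = 0.6.

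**3. What recording would and would not give**

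The documents give no exacerbation rate, so base risks of 10% to 40% over 6 months are assumed. For the other arm the risk is multiplied by 1.7. That factor is borrowed from Section 7's relative risk for overlap against COPD only. It is an illustration, not a treatment effect.

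Power with n = 20 per arm, two-sided 5%, is Φ{[d − 1.96√(2p̄(1 − p̄)/n)] / √[(p₁(1 − p₁) + p₂(1 − p₂))/n]}, where d = p₂ − p₁ and p̄ is the mean of p₁ and p₂. The 95% half-width for the risk difference, taking both arms at p₁, is 1.96√(2p₁(1 − p₁)/20).

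| Risk p₁ (assumed) | p₂ = 1.7p₁ | Power | n per arm for 80% | 95% half-width |
|---|---|---|---|---|
| 10% | 17% | 9% | 373 | 19 points |
| 20% | 34% | 16% | 157 | 25 points |
| 30% | 51% | 27% | 85 | 28 points |
| 40% | 68% | 42% | 49 | 30 points |

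If an arm of 20 had no events, the one-sided 95% upper limit would be 1 − 0.05^(1/20) = 13.9%.

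Recording the events would therefore give counts by arm and rough rates with wide intervals. It would not give a test of harm.

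**The case against.** The strongest reply is that this is a small mechanistic pilot whose aim, in Section 6, is RV hemodynamics and feasibility. Event counts in 20 per arm would add little precision, and reporting by arm is often left to the analysis plan. The first part is right about precision: step 3 shows that no test of harm is possible. The second part does not answer the point, because which events are collected, and in whom, is set here by an explicit endpoint list and visit schedule.

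A reader might draw several stronger conclusions that the text does not support.

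- **That the visits look only at compliance and discomfort.** They also include blood gas, questionnaires, cognitive tests and, at 6 months, nearly all the baseline tests, some of which could show certain harms.
- **That the pilot cannot inform the larger trial.** Compliance, feasibility and RVEDV with its variability all inform it. What is missing is event rates.
- **That the decision to proceed rests on RVEDV alone.** No such rule is stated. The protocol speaks only of encouraging results and has a long secondary list.
- **That contact stops after an exacerbation.** The stable-course rule governs invitations to visits. Telephone contact is promised throughout the study with no stability condition.
- **That Section 14 contradicts the background mortality by saying "we doubt any subject will need to be removed or excluded from the study".** That sentence opens by referring to the risk of the studies themselves. Section 7 describes mortality from the disease. Both can be true.

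**Conclusion.** The narrow point holds. The protocol lists no collection of exacerbations, hospitalisations or deaths in the randomised part, and treats an exacerbation only as a ground for not calling the patient for visits, while naming these same events as the outcomes of the trial to follow. Followed as written, the pilot yields no event counts by arm, and a difference in exacerbations between BiLevel and NOT could go unreported.

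This follows from the text and does not depend on the arithmetic. The expected deaths (about 1.2 in 40 at the untreated rate, 0.6 at the COPD-only rate) show only that such events are plausible within 6 months. They rest on a constant hazard over exactly 9 years. Because the stated median is over 9 years and every Part Two patient is assigned a treatment, the true figure may be lower. The number of exacerbations cannot be estimated from the protocol.

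The gap is worth closing because it is cheap to close and the data may not be recoverable afterwards. It does not invalidate the pilot's stated aims. No analysis plan was available, and Section 21 is absent from the text reviewed, so neither could be checked.

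**What to change.** - In Section 9, Study endpoints, add COPD exacerbations, all-cause hospitalisations and deaths from randomisation to 6 months as secondary (safety) endpoints. Count them for all 40 randomised patients, whether or not they are called for visits.
- In Section 9, Follow-up visits, state that these events are asked about and recorded at the planned visits and telephone contacts.
- Report counts by arm with exact confidence intervals, described as descriptive, and consider them alongside RVEDV when judging whether results are encouraging.
- Reconcile the Study Intervention and Follow-up visits paragraphs, so that it is clear what contact and data collection continue after an exacerbation.

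The cost is endpoint wording and a short event question in calls that Section 9 already puts at 5 to 10 minutes, so slightly more call time. The limit is that 20 per arm cannot test harm, and the report should say so.

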10. HUMAN SUBJECTS

We anticipate recruiting a total of 150 patients for phase one study: 50 patients with overlap syndrome, 50 patients with COPD, and 50 patients with OSA, age and gender matched to the overlap syndrome patients. For the phase two study, we aim to recruit 40 patients among the overlap syndrome patients who participated in phase one.

Phase One Study:

This group will include subjects with age > 18 years with known or suspected diagnosis of overlap syndrome, which we will define as COPD: Global Obstructive Lung Disease (GOLD) stage 2 disease or higher and OSA: apnea-hypopnea index (AHI) >15/hour. We will exclude patients already using oxygen or BiLevel/CPAP, patients with known or suspected renal failure (creatinine >1.5 mg/dl), pregnant women (due to possible risk to the fetus due to cardiac MRI and gadolinium contrast), patients with atrial fibrillation or frequent (>10/h) premature ventricular contractions (since these may complicate cardiac MRI sequences) and patients with known contraindications to MRI: metallic (ferromagnetic) implants, cardiac pacemakers, past history of claustrophobia. The control subjects will be divided into two groups, one with COPD only (50 subjects) and the other with OSA only (50 subjects). The COPD control group will include subjects with known COPD diagnosed by a pulmonologist (GOLD stage 2 or higher). The OSA control group will include subjects with a known diagnosis of OSA diagnosed by a sleep specialist (apnea-hypopnea index, AHI >15/hour). The exclusion criteria for the control subjects will be the same as the overlap syndrome subjects.

Phase Two Study:

40 patients in overlap syndrome group recruited during phase one study will be invited to participate in phase two study. The overlap syndrome patients who provide informed consent will be randomized into the two treatment arms (20 subjects in each treatment arm).

11. RECRUITMENT

The studies will be conducted during wakefulness and sleep in normal subjects, those with COPD and OSA. Males and females (18-79 years) will be studied. Equal numbers of men and women with OSA and controls will be recruited by research staff from the CTF Sleep Laboratory. Subjects will be recruited after they initiate contact in response to IRB approved standard posters, newspaper advertisements, and/or flyers. Subjects who initiate first contact will be followed up with a telephone screening to ensure they qualify for participation in the study. Patients who have indicated they would like to be involved in research to their primary care physician and verbally consented to being contacted for this purpose will be approached directly by a research coordinator. All participants will have an “opt-out” provision to avoid any possibility of coercion. Advertisement for this study will also be placed in appropriate locations in English and Spanish. Finally, if we sometimes have difficulty recruiting people of Hispanic ethnicity, advertisements will also be placed in regions of the community with a high Hispanic population. Recruitment advertisement text previously provided will be utilized for all modes of recruitment mentioned previously. If the provided text is to be changed, each recruitment item will be submitted to IRB for review and reapproval.

A flyer describing the study will also be placed in the waiting room of the UCSD Sleep and Pulmonary Clinic. Subjects will be screened for snoring (historically), body mass index (BMI), and history of COPD.

ResearchMatch will be used to contact prospective participants with IRB approved recruitment message, which is on a separate page labeled “ResearchMatch Message to Potential Participants.”

Spanish translated flyers and advertisements will be submitted after approval of the English documents.

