9. RESEARCH DESIGN AND METHODS

Part One Study Objective: The first part is a cross-sectional cohort study comparing subjects with overlap syndrome to those with COPD alone and those with OSA alone.

Subjects: Our target sample will be 150 subjects in the overlap syndrome group. This group will include subjects with age > 18 years with known or suspected diagnosis of overlap syndrome, which we will define as COPD: Global Obstructive Lung Disease (GOLD) stage 2 disease or higher and OSA: apnea-hypopnea index (AHI) >15/hour. We will exclude patients already using oxygen or BiLevel/CPAP, patients with known or suspected renal failure (creatinine >1.5 mg/dl), pregnant women (due to possible risk to the fetus due to cardiac MRI and gadolinium contrast), patients with atrial fibrillation or frequent (>10/h) premature ventricular contractions (since these may complicate cardiac MRI sequences) and patients with known contraindications to

MRI: metallic (ferromagnetic) implants, cardiac pacemakers, past history of claustrophobia.

The control subjects will be divided into two groups, one with COPD only (50 subjects) and the other with OSA only (50 subjects). The COPD control group will include subjects with known COPD diagnosed by a pulmonologist (GOLD stage 2 or higher). The OSA control group will include subjects with a known diagnosis of OSA diagnosed by a sleep specialist (apnea-hypopnea index, AHI >15/hour). The exclusion criteria for the control subjects will be the same as the overlap syndrome subjects.

Study enrollment: All patients will be recruited through the outpatient pulmonary and sleep medicine clinics at the UCSD hospitals. Poster advertisements will be placed in the outpatient clinics to encourage subject recruitment through physician referral. COPD patients in outpatient pulmonology clinics who express interest in enrolling in the study will be approached by one of the study investigators to obtain informed consent. COPD patients meeting eligibility criteria will be screened for OSA risk and scheduled for overnight polysomnography (PSG) as part of baseline visit. COPD patients with coexisting OSA will be enrolled in the overlap syndrome group. COPD patients without coexisting OSA will be enrolled in the COPD only control group. If COPD patients are referred for clinically indicated sleep studies, these patients will also be eligible for participation (as either COPD only or overlap syndrome patients), depending on the results of the sleep study.

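### Section 10 matches controls to the overlap group on age and gender while Section 11 sets equal numbers of men and women; the two agree only if the overlap group is half male, and no recruitment step ensures that

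*Protocol*

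**What the plan says.** Three sections of the protocol bear on who forms the groups in the cross-sectional part.

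- **Section 10 (Human Subjects)** lists the controls as "50 patients with COPD, and 50 patients with OSA, age and gender matched to the overlap syndrome patients". The modifier may cover both control groups or the OSA-only group alone.
- **Section 11 (Recruitment)** says "Equal numbers of men and women with OSA and controls will be recruited by research staff". It also says "Males and females (18-79 years) will be studied" and names normal subjects among those to be studied. Sections 9 and 10 require only age above 18, with no upper limit, and contain no normal group.
- **Section 9 (Research Design and Methods)** sets membership for COPD patients by the sleep study: "COPD patients with coexisting OSA will be enrolled in the overlap syndrome group" and "COPD patients without coexisting OSA will be enrolled in the COPD only control group". OSA-only controls enter by another route: "The OSA control group will include subjects with a known diagnosis of OSA diagnosed by a sleep specialist".

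No section states the sex mix of the overlap group, whether matching is individual or by frequency, the age tolerance, or which rule prevails. Section 9 names RVEDV as the primary endpoint both across the three groups and in the randomised part.

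**The concern.** Matching makes the controls' sex mix follow the overlap group. An equal-numbers rule fixes it at one half whatever the overlap group looks like. Staff cannot satisfy both unless the overlap group happens to be balanced.

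The three-group comparison is not randomised, so group composition is one of its main protections against confounding. RVEDV is named as a volume without indexing to body size, whereas RV mass is listed as an index. If RVEDV differs between men and women, a difference in sex mix created by recruitment would show up as a difference between diseases. A report could also describe as matched a control group that was recruited to a different rule.

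**Working it through.** The protocol gives no sex mix, sex difference in RVEDV, standard deviation or significance level, so there is no figure of its own to reproduce. The check has three parts.

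**1. Can the sex rules hold together?** Let p be the male share of the overlap group. Section 10 requires a male share of p in the matched controls; Section 11 requires 0.5. Both hold only when p = 0.5. Section 9 takes overlap patients as the sleep study identifies them, with no quota, so p is left free.

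**2. What could the mismatch do to RVEDV?** All inputs here are assumptions:
- p = 0.6 to 0.8 in the overlap group, and 0.5 in controls recruited to Section 11;
- a male–female gap g of 0.5 to 0.8 SD in RVEDV;
- a two-sided 5% test without adjustment for sex.

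Spurious difference = (p − 0.5) × g.
- Low end: 0.10 × 0.5 = 0.05 SD.
- High end: 0.30 × 0.8 = 0.24 SD.

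For a two-sample t-test with unit SD, the noncentrality is the shift divided by √(1/n₁ + 1/n₂). With 50 against 50, the denominator is √(2/50) = 0.20.

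| Shift (SD) | Noncentrality | False rejection, 50 vs 50 |
|---|---|---|
| 0 | 0 | 5.0% |
| 0.05 | 0.05/0.20 = 0.25 | 5.7% |
| 0.24 | 0.24/0.20 = 1.20 | 22.1% |

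The result is somewhat sensitive to how the SD is defined. If g is in within-sex SD units and the between-sex variance is added, the standard error at the high end is √[(1 + 0.8×0.2×0.8²)/50 + (1 + 0.25×0.8²)/50] = √(2.2624/50) = 0.213. The normal test then rejects about 20% of the time instead of 22%.

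Section 9 elsewhere states "Our target sample will be 150 subjects in the overlap syndrome group", against 50 in Section 10. With 150 against 50, the t-test rates become 6.1% and 31.0%. That size discrepancy is a separate matter, and the 50-per-group figures are used here.

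**3. Does assignment by sleep study rule out matching?** No. It fixes disease status; matching concerns which eligible patients are then kept. To select 50 COPD-only controls with male share p from a pool with male share q, the expected number of sleep-study-negative patients is the larger of 50p/q and 50(1 − p)/(1 − q). For example, q = 0.5 and p = 0.8 gives max(80, 20) = 80. Over assumed q = 0.4–0.6 and p = 0.5–0.8, the requirement is about 50 to 100. Matching is therefore feasible at the cost of extra screening, but no section describes the selection.

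**The case against.** A reader might infer that three rules contradict one another and that the matching cannot be delivered. The protocol does not support that. The direct conflict is between Sections 10 and 11. Section 9 leaves matching without a mechanism but does not forbid it, and its sleep-study rule does not govern the OSA-only group.

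The other points against the concern are these.

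- **Overlap patients have OSA by definition.** If the Section 11 sentence is meant to include them, every group would be half male and the sex conflict would disappear. That reading is possible. It would, however, put a sex quota on overlap patients that the enrolment route in Section 9 does not contain, and it would still leave age matching without a method.
- **Section 11 may be text carried over from another study.** It refers to normal subjects, whom this design does not include, so its controls may not be the COPD-only and OSA-only groups. This weakens the case that anyone intended the quota. It remains the section that tells staff whom to recruit, so it needs correcting either way.
- **Section 10 may promise matching for OSA-only alone.** That stands. On this reading COPD-only carries no matching claim, and the protocol should say so.
- **The analysis may adjust for sex.** A statistical analysis plan may exist and is not shown, so the absence of adjustment or indexing from the protocol is not counted as a fault. Adjustment would remove most or all of the sex bias. It would not settle which recruitment rule applies or make a matching statement true.
- **The upper error rate needs both assumptions at their extremes and an unadjusted test.** That also stands. At the low end the error rate is close to nominal.

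**Conclusion.** The concern holds in a limited form. The sex-composition rules in Sections 10 and 11 are inconsistent unless the overlap group is half male, and the enrolment route in Section 9 neither makes it so nor contains a matching step. The age limits also differ between sections.

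The consequence is possible confounding by sex in the cross-sectional RVEDV comparison. It requires three things: a sex imbalance in the overlap group, a sex difference in RVEDV, and no adjustment. Its size cannot be known from the documents. Under the stated assumptions it is 0.05–0.24 SD, with about 6% to 22% false rejection at 50 against 50. If the overlap group is balanced, or the controls truly follow its sex mix, the sex bias is zero.

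It would be tempting to say that the primary result of the trial is biased. The documents do not support that: the randomised BiLevel versus oxygen comparison takes place within the overlap group and is not affected. The correction should be made, and preferably before enrolment, because group composition is hard to repair afterwards.

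**What to change.** - In Section 11, delete the equal-numbers sentence and the reference to normal subjects.
- Keep one rule for OSA-only controls: frequency matching to the overlap group by sex and age band, filled in step with that group.
- For COPD-only, either add a selection step among patients without OSA on the sleep study or state that the group is not matched.
- Give one age range and use it in Sections 9, 10 and 11.
- Compare RVEDV across the three groups with adjustment for age, sex, height and weight. Height and weight are measured at the baseline visit, and matching already requires age and sex. If an analysis plan already provides for this, a cross-reference is enough.

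The cost is protocol wording and an adjusted comparison, with no new data. OSA-only recruitment may be slightly slower while the sex and age cells fill. A selection step for COPD-only, if chosen, would add screening; declaring that group unmatched would not.
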